5.3. Lifestyle Considerations

Participants are not allowed to use tanning beds within 8 weeks prior to Day 1 and during the study.

Participants are not allowed to use dihydroxyacetone (generally present in self-tanning products) within 4 weeks prior to Day 1 and during the study.

Participants are allowed to use of bland emollients, camouflage makeups, or sunscreen agents.

5.3.1. Meals and Dietary Restrictions

Participants must abstain from consumption of grapefruit or grapefruit juice (pomelos, exotic citrus fruits, grapefruit hybrids, or fruit juices) and of Seville oranges from 14 days before the start of study drug until after the final dose of study drug.

Participants must abstain from consumption of dietary supplements containing St John's wort (*Hypericum perforatum*) from 14 days before the start of study drug until after the final dose of study drug.

5.4. Screen Failures

Screen failures are defined as participants who consent to participate in the clinical study but are not subsequently randomly assigned to study drug.

Tests with results that fail eligibility requirements may be repeated once during screening if the investigator believes the result to be in error. Additionally, a participant who fails screening may repeat the screening process 1 time if the investigator believes that there has been a change in eligibility status. Participants who rescreen must reconsent and be assigned a new participant number.

5.5. Replacement of Participants

No participants will be replaced at any time during this study. However the COVID-19 global pandemic may present challenges to the normal conduct of this study, requiring the outline of potential mitigation strategies described in [Appendix E](#).

5.6. Data Safety Monitoring Board

This study will use an external DSMB to monitor safety. There will be 1 planned DSMB review following randomization of the initial 40 participants in the study and their respective completion of visit at Week 24, with at least 2 additional reviews at a time to be determined after the first assessment. The DSMB members will be blinded to participants' treatment assignment for the initial safety review; however, the DSMB members may request unblinding at any time.

Participants and investigators will remain blinded to each participant's treatment assignment during both the placebo-controlled and extension periods of the study. The sponsor will remain blinded through completion of the placebo-controlled period. The sponsor will be unblinded after the primary database lock, when all participants have completed the placebo-controlled, double-blind treatment period (Week 24 analysis).

The voting members of the committee are external to the sponsor. The members of the DSMB will not be involved with the study in any other way (eg, they cannot be study investigators) and will have no competing interests that could affect their roles with respect to the study.

[figure not shown]
The DSMB will make recommendations to the sponsor regarding steps to ensure both participant safety and the continued ethical integrity of the study. Specific details regarding composition, responsibilities, and governance, including the roles and responsibilities of the various members of the clinical study team, and requirements for the proper documentation of DSMB reports, minutes, and recommendations will be described in the DSMB charter that is reviewed and approved by all DSMB members.

6. STUDY TREATMENT

6.1. Study Treatments Administered

Information regarding study drug and administration is provided in [Table 8](#). Participants will record study drug administration in a daily diary. Further information regarding study drug administration is provided in [Appendix C](#).

The COVID-19 global pandemic may present challenges to the normal conduct of this study, requiring the outline of potential mitigation strategies described in [Appendix E](#).

6.2. Preparation, Handling, and Accountability

The investigator or designee must confirm appropriate temperature conditions have been maintained during transit for all study treatments received and any discrepancies are reported and resolved before use of the study treatment.

Only participants enrolled in the study may receive study treatment, and only authorized site staff may supply or administer study treatment. All study treatment must be stored in a secure, environmentally controlled, and monitored (manual or automated) area in accordance with the labeled storage conditions with access limited to the investigator, and authorized site staff.

The investigator (or designee) is responsible for study treatment accountability, reconciliation, and record maintenance (ie, receipt, reconciliation, and final disposition records). Inventory and accountability records must be maintained and readily available for inspection by the study monitor and are open to inspection at any time by any applicable regulatory authorities. The investigator or designee must maintain records that document:

- Delivery of study drug to the study site.
- Inventory of study drug at the site.
- Participant use of the study drug, including tablet counts from each supply dispensed.
- Return of study drug to the investigator or designee by participants.

The investigational product must be used only in accordance with the Protocol (see [Appendix C](#)). The investigator will also maintain records adequately documenting that the participants were provided the specified study drug. These records should include dates, quantities, and any available batch or serial numbers or unique code numbers assigned to the investigational product and study participants.

Completed accountability records will be archived by the site. The investigator or designee will be expected to collect and retain all used, unused, and partially used containers of study drug until verified by the study monitor (unless otherwise agreed to by the sponsor). At the conclusion of the study, the investigator or designee will oversee shipment of any remaining study drug back to the sponsor or its designee for destruction according to institutional SOPs. If local procedures mandate on-site destruction of the investigational supply, the site should (where local procedures allow) maintain the investigational supply until the study monitor inspects the accountability records in order to evaluate compliance and accuracy of accountability by the investigative site. At sites where the study drug is destroyed before monitor inspection, the monitors rely on documentation of destruction per the site SOP.

Further guidance and information for the final disposition of unused study treatments are provided in the Pharmacy Manual.

The COVID-19 global pandemic may present challenges to the normal conduct of this study, requiring the outline of potential mitigation strategies described in [Appendix E](#).

6.3. Measures to Minimize Bias: Randomization and Blinding

All participants will be centrally assigned to study treatment using an IRT system (see Section 8.1.3). Participant randomization will be stratified based on total BSA involvement (8%-20% and > 20%). Once a randomization number has been assigned, it must not be reassigned. Full details will be provided in the IRT Study Reference Manual.

Study drug will be dispensed at study visits summarized in the SoA (see Table 3 and Table 4).

Returned study drug should not be redispensed to participants.

Participants and investigators will remain blinded to each participant's treatment assignment during both the placebo-controlled and extension periods of the study. The sponsor will remain blinded through completion of the placebo-controlled period. The sponsor will be unblinded after the primary database lock, when all participants have completed the placebo-controlled, double-blind treatment period (Week 24 analysis). Emergency unblinding will occur if an AE requires the investigator to be made aware of the participant's treatment assignment (see emergency unblinding procedures in Section 9.6 and refer to the IRT Manual).

6.4. Study Treatment Compliance

Compliance with all study-related treatments should be emphasized to the participant by the site personnel, and appropriate steps should be taken to optimize compliance during the study.

Compliance with study drug will be monitored by the study site based on the drug accountability and reported in the eCRF. Participants will be instructed to bring all unused study drug with them to study visits in order for site personnel to conduct tablet counts to assess study drug accountability.

Participant's compliance must be within 80% to 120%, assessed at each study visit. If outside of this range, it will be considered a protocol deviation. Participants consistently noncompliant with the study drug may be withdrawn from the study. The decision on withdrawal will be made by the investigator after consultation with the sponsor, and relevant correspondence will be archived in the site study file.

[figure not shown]

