1. PROTOCOL SUMMARY

Protocol Title: A Phase 2, Randomized, Double-Blind, Placebo-Controlled, Dose-Ranging Study of the Efficacy and Safety of INCB054707 Followed by an Extension Period in Participants With Vitiligo

Protocol Number: INCB 54707-205

Objectives and Endpoints:

[Table 1](#) presents the primary and key secondary objectives and endpoints.

Table 1: Primary and Secondary Objectives and Endpoints

Objectives	Endpoints
Primary	
To determine the efficacy of INCB054707.	Percent change from baseline in Total Vitiligo Area Scoring Index (T-VASI) at Week 24.
Key Secondary	
To further determine the efficacy of INCB054707.	Proportion of participants achieving T-VASI50 at Week 24. T-VASI50 is defined as 50% or greater reduction in the Total Vitiligo Area Scoring Index.

Overall Design:

[Table 2](#) presents the key study design elements. Further study details are presented after the table.

[figure not shown]
Table 2: Key Study Design Elements

Study Phase	Phase 2
Clinical Indication	Treatment of adult patients with vitiligo.
Population	Men or women aged 18 to 75 years with nonsegmental vitiligo who have depigmented areas including T-BSA \geq 8%, T-VASI \geq 8, F-BSA \geq 0.5%, and F-VASI \geq 0.5.
Number of Participants	Approximately 160 participants will be randomized 1:1:1:1 to receive 1 of 3 doses of INCB054707 or placebo. The 28-week double-blind extension period will include all participants who successfully complete the placebo-controlled period.
Study Design	This is a Phase 2, randomized, double-blind, placebo-controlled, dose-ranging, multicenter study to evaluate the efficacy and safety of INCB054707 (15, 45, and 75 mg QD) over a 24-week treatment period, followed by a 28-week double-blind extension period (45 mg and 75 mg QD) and a 24-week follow-up period. Participants will be stratified based on total BSA involvement (8%-20% and $>$ 20%).
Estimated Duration of Study Participation	Screening: Up to 32 days Placebo-controlled period (double-blind): 24 weeks Extension period (double-blind): 28 weeks Safety follow-up: 4 weeks after last dose of study drug [REDACTED] [REDACTED] Total: Up to approximately 80 weeks (19 months)
DSMB	Yes (external)
Coordinating Principal Investigator	[REDACTED], MD

Treatment Groups and Duration:

The study design is shown in [Figure 1](#). The SoA for the placebo-controlled and extension periods are detailed in [Table 3](#) and [Table 4](#), respectively.

Figure 1: Study Design Schema

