Table 4: Schedule of Activities (Extension Period)

Visit Day (Range)	Treatment (Extension Period)									Safety Follow-Up	Notes
	Wk 26 (± 3 d) (Remote Visit)	Wk 28 (± 3 d)	Wk 30 (± 3 d) (Remote Visit)	Wk 32 (± 3 d)	Wk 36 (± 3 d)	Wk 40 (± 3 d)	Wk 44 (± 3 d)	Wk 48 (± 3 d)	Wk 52 (± 3 d) (EOT2)		
Administrative procedures											
Concomitant medications	X	X	X	X	X	X	X	X	X	X	Section 6.6 and Section 8.1.5
Contact IRT		X		X	X	X	X	X	X		Section 8.1.3
Distribute reminder cards and diaries		X		X	X	X	X	X	X		Section 8.1.4
Dispense study drug		X		X	X	X	X	X			Section 6.2
Collect study drug and review diary cards		X		X	X	X	X	X	X		Section 8.1.4
Assess study drug compliance		X		X	X	X	X	X	X		Section 6.4
Safety assessments											
AE assessments	X	X	X	X	X	X	X	X	X	X	Section 8.3.1
Comprehensive physical examination									X		Section 8.3.2
Weight									X		Section 8.3.2
Targeted physical examination		X		X	X	X	X	X		X	Section 8.3.2
Vital signs		X		X	X	X	X	X	X	X	Section 8.3.3
12-lead ECG									X		Section 8.3.4

Table 4: Schedule of Activities (Extension Period) (Continued)

Visit Day (Range)	Treatment (Extension Period)									Safety Follow-Up	Notes	
	Wk 26 (± 3 d) (Remote Visit)	Wk 28 (± 3 d)	Wk 30 (± 3 d) (Remote Visit)	Wk 32 (± 3 d)	Wk 36 (± 3 d)	Wk 40 (± 3 d)	Wk 44 (± 3 d)	Wk 48 (± 3 d)	Wk 52 (± 3 d) (EOT2)			
Efficacy assessments												
T-VASI		X		X	X	X	X	X	X	X	X	Section 8.2.2
Photography of the face					X				X			Section 8.2.6
Photography of nonfacial targeted areas					X				X			Section 8.2.6

Table 4: Schedule of Activities (Extension Period) (Continued)

Visit Day (Range)	Treatment (Extension Period)									Safety Follow-Up	Notes
	Wk 26 (± 3 d) (Remote Visit)	Wk 28 (± 3 d)	Wk 30 (± 3 d) (Remote Visit)	Wk 32 (± 3 d)	Wk 36 (± 3 d)	Wk 40 (± 3 d)	Wk 44 (± 3 d)	Wk 48 (± 3 d)	Wk 52 (± 3 d) (EOT2)		
Laboratory assessments											
Serum pregnancy test (WOCBP)									X	X	Section 8.3.5.1 and Table 13
Urine pregnancy test (WOCBP)		X		X	X	X	X	X			Section 8.3.5.1 and Table 13
Urinalysis					X			X	X		Table 13
Hematology and blood chemistry assessments	X	X	X	X	X	X	X	X	X		Table 13 ; at-home blood collection for remote visits.
Coagulation		X									Reflexive testing during the study per Appendix D (also Table 13).
Lipid panel					X				X		Table 13
Thyroid function markers					X		X		X	X	Table 13
Inflammation marker					X					X	Table 13

^a Only for participants who consent to additional follow-up visits.

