2.2.1. Scientific Rationale for Study Design

INCB054707 is an oral small-molecule JAK1 inhibitor and has been evaluated in 36 participants with HS in 2 clinical studies with oral doses of up to 90 mg for 8 weeks. During the treatment period, INCB054707-treated participants demonstrated improvement, characterized as decreased number of abscesses and inflammatory nodules, decreased HS-associated pain, and improved quality of life. Observed AEs were mild to moderate in intensity and mostly unrelated to study medication, with no associated SAEs or withdrawals. Immunological commonalities exist between HS and vitiligo, in which lesions have increased expression of lymphocyte-recruiting chemokines, including CXCL10 (Vosseen et al 2019), and elevated IFN- γ levels (Banerjee et al 2017). Treatment of patients with vitiligo for 24 weeks with the topical JAK1/2 inhibitor ruxolitinib cream demonstrated that inhibition of the JAK-STAT pathway leads to repigmentation (Rosmarin et al 2020). [REDACTED]

[REDACTED]

[REDACTED]

[REDACTED]

In the proposed study, the clinical safety and efficacy of 3 doses of INCB054707 (15, 45, and 75 mg) compared with placebo will be evaluated in male and female adult participants with extensive vitiligo (T-BSA \geq 8%, T-VASI \geq 8, F-BSA \geq 0.5%, and T-VASI \geq 0.5) for 24 weeks, which is consistent with the duration of other systemic therapies and with narrow-band UVB phototherapy (Hamzavi et al 2004). Efficacy will be assessed via changes in the [REDACTED] affected by vitiligo lesions, [REDACTED] and T-VASI, [REDACTED] and photography. [REDACTED]

[REDACTED]

[REDACTED]

[REDACTED]

[REDACTED]

With the goal of obtaining long-term efficacy and safety data for the compound (up to 52 weeks in total), after the 24-week placebo-controlled period, all participants will enter into a double-blind extension period for 28 weeks and will receive either 45 mg or 75 mg QD, followed by a 4-week safety follow-up period [REDACTED]

[REDACTED] to monitor safety and potential change in pigmentation after discontinuation or completion of treatment with INCB054707.

It is expected that the outcome of this study will be instrumental in informing dose selection to be evaluated in a potential Phase 3 study in the future.

[REDACTED]

[REDACTED]

[REDACTED]

[REDACTED]

[REDACTED]

[REDACTED]

[REDACTED]

[REDACTED]

[REDACTED]

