7. DISCONTINUATION OF STUDY TREATMENT AND PARTICIPANT WITHDRAWAL

7.1. Discontinuation of Study Treatment

7.1.1. Reasons for Discontinuation

Participants **must** be discontinued from study treatment for the following reasons:

- The participant becomes pregnant.
- Consent is withdrawn.
Note: Consent withdrawn means that the participant has explicitly indicated that he/she does not want to be followed any longer; in this case, no further data, except data in the public domain, may be solicited from or collected on the participant. Participants may choose to discontinue study treatment and remain in the study.
- Further participation would be injurious to the participant's health or well-being, in the investigator's medical judgment.
- Any AE of unacceptable severity as noted in Section [6.5](#).
- Participant meets discontinuation criteria as described in Section [6.5](#).
- The study is terminated by the sponsor.
- The study is terminated by the local health authority, IRB, or IEC.

A participant **may** be discontinued from study treatment as follows:

- If, during the course of the study, a participant is found not to have met eligibility criteria, the medical monitor, in collaboration with the investigator, will determine whether the participant should be withdrawn from study treatment.
- If a participant is noncompliant with study procedures or study drug administration in the investigator's or sponsor's opinion, the sponsor should be consulted for instruction on handling the participant.

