7.1.2. Discontinuation Procedures

In the event that the decision is made to permanently discontinue the study treatment, the EOT visit (EOT1 during the placebo-controlled period; EOT2 during the extension period) should be conducted. Reasonable efforts should be made to have the participant return for a safety follow-up visit 4 weeks after last dose (EOS) [REDACTED].

[REDACTED]. These visits are described in [Table 3](#) and [Table 4](#).

The last date of the last dose of study drug and the reason for discontinuation of study drug will be recorded in the eCRF.

If a participant is discontinued from study treatment:

- The study monitor or sponsor must be notified.
- The reason(s) for discontinuation must be documented in the participant's medical record and the primary reason for discontinuation must be included in the eCRF.
- The EOT visit should be performed and date recorded.
- The status of the participant should be updated to EOT in the IRT.
- Participants must be followed for safety until the time of the follow-up visit or until study drug-related toxicities resolve, return to baseline, or are deemed irreversible, whichever is longest.

If the participant discontinues study treatment and actively withdraws consent for collection of follow-up data (safety follow-up or disease assessment), then no additional data collection should occur; however, participants will have the option of withdrawing consent for study treatment but continuing in the follow-up period of the study for safety/efficacy assessments.

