7.2. Participant Withdrawal From the Study

A participant may withdraw from the study at any time at his/her own request or may be withdrawn at any time at the discretion of the investigator for safety, behavioral, compliance, or administrative reasons. When a participant is withdrawn from the study, the EOT visit procedures should be performed; if possible, the safety follow-up visit should also be conducted within 28 (+ 7) days of the last dose of study drug [REDACTED].

If a participant withdraws from the study, he/she may request destruction of any samples taken and not tested, and the investigator must document this in the site study records. If the participant withdraws consent for disclosure of future information, the sponsor may retain and continue to use any data collected before such a withdrawal of consent.

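### Protocol 6.4 and 7.2 allow study withdrawal for drug noncompliance while consent stands, which can lose the Week 24 T-VASI when last dose is at or before Week 16

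*Protocol*

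**What the plan says.** Protocol 6.4 sets a compliance range of 80% to 120%, checked at each visit, and then provides: "Participants consistently noncompliant with the study drug may be withdrawn from the study". The investigator decides after consulting the sponsor. Protocol 7.2 adds that a participant "may be withdrawn at any time at the discretion of the investigator for safety, behavioral, compliance, or administrative reasons".

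For a participant withdrawn from the study, 7.2 asks for the end-of-treatment procedures (EOT1 in this period) and then: "if possible, the safety follow-up visit should also be conducted within 28 (+ 7) days of the last dose of study drug". The text after that clause is redacted. No visible sentence asks a withdrawn participant to return at Week 24.

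The primary endpoint is percent change in T-VASI at Week 24, and the key secondary endpoint is T-VASI50 at Week 24 (Protocol Section 3; SAP 7.4 and 7.5). SAP 5.3.2 uses the ITT population, meaning everyone randomised, for all efficacy data in the placebo-controlled period.

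Three visible texts bear on later follow-up. The summary describes treatment "followed by a 28-week double-blind extension period (45 mg and 75 mg QD) and a 24-week follow-up period". Section 2.2.1 gives the purpose of follow-up as "to monitor safety and potential change in pigmentation after discontinuation or completion of treatment with INCB054707". A footnote to Table 4 reads "Only for participants who consent to additional follow-up visits". The schedule of the added visits is redacted.

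**The concern.** Taking too few tablets is a post-randomisation event, and it may be related to tolerability, perceived lack of effect or engagement with the trial. An ITT analysis is meant to keep such participants and their outcomes. Here the plan lets the investigator end study participation, and not just dosing, for someone who is still willing to be assessed.

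At stake is the one measurement that supports both the primary and the key secondary endpoint. A value lost because consent is withdrawn cannot be prevented by the protocol; a value lost by the investigator's choice while consent stands can be. SAP 7.4.3 lists no sensitivity or supportive analyses for the primary endpoint, so preventing the loss matters more than it otherwise would. The protocol itself treats this visit as essential: under the pandemic provisions in Appendix E, Week 24 must take place in person for efficacy assessment even if it falls outside the visit window.

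**Working it through.** The check is whether the visits asked for after withdrawal can supply a Week 24 T-VASI. There is no stated figure to reproduce, because sample size and primary analysis are redacted.

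**Inputs.** Visit windows are ±3 days (Protocol Table 3). The safety visit is 28 to 35 days after last dose (7.2). Compliance is assessed at Weeks 4, 8, 12, 16 and 20 (Table 3). I number days as in SAP 4.1.2, so the Week *w* visit is nominally Day 7*w* + 1, and I take last dose to be on the day of the visit.

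**Week 24 window.** 7 × 24 + 1 = Day 169; ±3 gives Days 166 to 172.

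**Safety visit.** Earliest = (7*w* + 1 − 3) + 28; latest = (7*w* + 1 + 3) + 35.

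| Last dose at | Visit days | Safety visit days | Can fall in Days 166–172? |
|---|---|---|---|
| Week 4 | 26–32 | 54–67 | No |
| Week 8 | 54–60 | 82–95 | No |
| Week 12 | 82–88 | 110–123 | No |
| Week 16 | 110–116 | 138–151 | No, short by at least 166 − 151 = 15 days |
| Week 20 | 138–144 | 166–179 | Yes |

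In general, a last dose on or before Day 130 cannot reach the window, since 130 + 35 = 165. Week 16 is the last scheduled clinic visit for which this holds.

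**When the route can first apply.** If *consistently* in 6.4 means at least two visits (my assumption), the earliest exit under 6.4 is Week 8. Section 7.2 has no such limit.

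**Distance from the last requested visit to Week 24.** With EOT1 only, 24 − *w*: 16, 12 and 8 weeks for exit at Weeks 8, 12 and 16. If the 4-week visit is attended and includes T-VASI, 24 − (*w* + 4): 12, 8 and 4 weeks. These are upper limits, because later visits may exist in redacted text.

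**Extended follow-up.** If it ran 24 weeks from exit, it would end at *w* + 24, that is Week 32, 36 or 40. It would therefore span Week 24, but no visible text places a T-VASI there.

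**Scale, on assumed losses.** With about 40 per arm (SAP 3.1), losing 2 or 4 values in each arm raises the standard error of a simple two-group comparison by √(40/38) = 1.026 or √(40/36) = 1.054. Lost precision would be small; the concern is that the loss need not be random.

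**The case against.** The strongest reply is that the decisive text is redacted. Sections 7.1.2, 7.2, 8.7 and 8.8.1 all have blacked-out text about follow-up visits, Amendment 4 lengthened follow-up, and 2.2.1 says pigmentation is to be monitored after discontinuation. A T-VASI near Week 24 may well be scheduled for participants who agree to it. This stands, and it is why the claim is that the value can be lost. A reader might infer that it always is; the documents do not support that. EOT1 also includes a T-VASI, so what is at risk is the Week 24 value and not all post-baseline data.

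A reader might also infer a contradiction with 7.1.1, which opens an entry under possible treatment discontinuation with "If a participant is noncompliant with study procedures or study drug administration". There is none. That entry leaves handling to the sponsor's instruction and does not rule out study withdrawal. Nor would a treatment stop by itself secure the value: the visible visits in 7.1.2 are the same, and what it adds is that "participants will have the option of withdrawing consent for study treatment but continuing in the follow-up period of the study for safety/efficacy assessments". Post-treatment follow-up is therefore the wider issue, and it applies equally to stops for adverse events. The fix has to cover all of them.

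There are real safeguards. The 6.4 route is optional, needs consistent noncompliance and sponsor consultation, and operates while investigator and sponsor are blinded (6.3). SAP 6.2 tabulates withdrawals with reasons. These limit arm-selective use and make the loss visible, but they do not restore the measurement.

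Finally, the hidden analysis may deal adequately with missing values. MMRM (both documents) and nonresponder imputation (SAP) appear in the abbreviation lists, though neither is visibly tied to an endpoint.

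**Conclusion.** The point holds as a modest design improvement, worth considering, with medium confidence. The visible rules permit study withdrawal for drug noncompliance without withdrawn consent, and for last dose at or before Week 16 the visits then asked for do not reach the Week 24 window. The primary and key secondary value can be lost for a reason the protocol could remove.

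The timing rests on last dose falling at a scheduled visit and on the safety visit occurring within its stated 28 to 35 days. Exit at Week 20 loses little if the safety visit is attended and T-VASI is done there.

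A reader might go further and infer a biased treatment comparison. The documents do not support that: they give no frequency of such withdrawals, and the primary analysis and missing-data method are redacted, so neither size nor direction can be stated.

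**What to change.** Make three wording changes:

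- **6.4:** change the permitted consequence of consistent drug noncompliance from withdrawal from the study to discontinuation of study treatment, and let the sentence on who decides refer to that discontinuation.
- **7.2:** keep compliance as a ground where it concerns study procedures, and add: *Noncompliance with study drug alone is not a reason for withdrawal from the study.*
- **7.1.2:** add: *A participant who stops study treatment during the placebo-controlled period, for noncompliance or any other reason, and who has not withdrawn consent is asked to attend the scheduled T-VASI visits through Week 24.*

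The compliance range, the rules for stopping or restarting drug and the right to withdraw consent stay as they are.

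The cost is a few visits already in Table 3: four (Weeks 12, 16, 20 and 24) for a stop at Week 8, three for Week 12 and two for Week 16. Attendance can be requested but not compelled. If off-treatment values enter the analysis, the observed effect may be slightly diluted; if the analysis excludes them, the primary result is unchanged and the values are simply on record.
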